## STUDY OBJECTIVE

**The combination treatment of topicals and systemic medications in psoriasis has been traditionally used by community dermatologists. However, there is no significant data from clinical studies to reveal the additional benefit of the combination since all registration studies have to be done as monotherapy. It will be very useful data for practicing dermatologist to show the additional benefit of Lexette and Sorilux in the beginning and then maintenance treatment of Sorilux alone in moderate plaque type psoriasis patients.**

### 1.1 Primary Endpoint

To observe the efficacy and safety of Lexette and Sorilux in moderate plaque type psoriasis for 2 weeks and then maintenance of success compared to vehicle with Sorilux for the next 6 weeks. Primary endpoint is the percent of subjects who maintain clear or almost clear on PGA at week 8.

#### Secondary Endpoints:

PGA at week 2

VAS at week 2 and week 8

DLQI at week 2 and week 8

TLSS at week 2 and week 8

## 2 STUDY DESIGN

This is a single-center, double-blind study. Approximately 30 qualified subjects will be enrolled into a 8 weeks study. Subjects will be randomized to study treatment at a 1:1 ratio: of Lexette plus Sorilux for 2 weeks versus Lexette plus vehicle for 2 weeks. Those subjects who are clear or almost clear at the end of 2 weeks will be re-randomized into Sorilux for 6 weeks versus vehicle for 6 weeks at 1:1 ratio. All adverse events and con meds will be recorded throughout the study.

Group A n = 15	Lexette + Sorilux for 2 weeks
Group B n = 15	Lexette + plus Vehicle Foam for 2 weeks

Subjects will attend a Screening Visit/Baseline visit and if found eligible will be randomized to study treatment. Patients will be counselled on the use of the study medication and the medications will be labelled for the appropriate group as noted above.

Total study period is 8 weeks. Study visits will be, screening/baseline, week 2 and week 8. Study assessments will be at each visit: BSA, PGA, Itch VAS, DLQI, and TLSS in addition to standard medical assessments. There will be a standard prohibited medication/treatment and washout periods.

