### 4.2.2 Treatment Assignment

All subjects who have signed an ICF will receive a 2-digit subject number, starting at 01. This subject number will be used to identify the subject throughout the study. When subjects qualify for the study, they will be randomized to study treatment groups utilizing treatment assignment numbers (TANs). Therefore, TANs are not the same as subject numbers. The next eligible subject will receive the lowest available TAN. The schedule will be prepared on a balanced 1:1 basis and will be available only to the member(s) of the site staff that is responsible for dispensing study treatment to the subject. Subjects withdrawn from the study will retain their subject number and their TAN, if

already allocated. New subjects will be allotted a new subject number and, if applicable, a new TAN.

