### **7.2 Analyses**

Statistical analyses will be conducted on an intent-to-treat population that includes all subjects who were enrolled and received study medication. Due to small sample size and exploratory nature of the study, descriptive statistics will be performed using SAS. Any additional statistical analyses will be performed as appropriate and detailed in the final report. All statistical tests will be two-sided and interpreted at a 5% significance level. Descriptive statistics (i.e., mean, standard deviation, etc.) will be provided for all continuous variables and frequencies for all categorical variables collected in this study. Summary tables will be used to present patient population characteristics at Baseline; data from the study questionnaires will be included. Analyses of study treatment will be performed using an ANCOVA technique with the Baseline value as the covariate provided the necessary assumptions for parametric tests are satisfied. The Wilcoxon Rank-Sum test will be used if the necessary assumptions for parametric tests are not satisfied. Mean scores will also be analyzed. Safety analyses will be performed in terms of incidence and severity of local tolerance signs and symptoms and adverse and/or unexpected events.

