## Physicians Global Assessment Psoriasis

\_\_\_ 0. Clear: no signs of psoriasis (Hyper/hypopigmentation changes alone are acceptable).  
Plaque elevation = 0. Scaling = 0. Erythema = +/- (hyperpigmentation, pigmented macules,  
diffuse faint pink or red coloration).

\_\_\_ 1. Almost Clear: Plaque elevation = +/- (possible but difficult to ascertain whether there  
is slight elevation above normal skin). Scaling = +/- (surface dryness with some white  
discoloration). Erythema = up to moderate (up to definite red coloration).

\_\_\_ 2. Mild: Plaque elevation = slight (slight but definite elevation, typically edges are  
indistinct or sloped). Scaling = fine (fine scale partially or mostly covering lesions). Erythema  
= up to moderate (up to definite red coloration).

\_\_\_ 3. Moderate: Plaque elevation = moderate (moderate elevation with rough or sloped  
edges). Scaling = coarse (coarse scale covering most or all of the lesions). Erythema =  
moderate (definite red coloration).

\_\_\_ 4. Severe: Plaque elevation = marked (marked elevation typically with hard or sharp  
edges). Scaling = coarse (coarse, nontenacious scale predominates, covering most of all  
lesions). Erythema = severe (very bright red coloration).

[figure not shown]

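### Cheap improvement: stratify the week-2 re-randomisation by week-2 PGA (clear v almost clear) and report the week-8 result by that grade

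*Combined protocol and SAP*

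**What the plan says.** Section 2 plans a small trial: "Approximately 30 qualified subjects will be enrolled into a 8 weeks study", 15 per initial group. At week 2, "Those subjects who are clear or almost clear at the end of 2 weeks will be re-randomized into Sorilux for 6 weeks"; the alternative is vehicle over the same period, with equal allocation. Both qualifying grades go into that step together and no stratification factor is named.

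Section 1.1 defines the primary outcome: "Primary endpoint is the percent of subjects who maintain clear or almost clear on PGA at week 8". The two grades are pooled here as well.

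Section 4.2.2 says "The schedule will be prepared on a balanced 1:1 basis". In context this concerns assignment when a subject qualifies for the study. How the week-2 re-randomisation list is made is not described.

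For analysis, section 7.2 says "Analyses of study treatment will be performed using an ANCOVA technique with the Baseline value as the covariate", with a rank-sum test as the alternative. It names no method for the binary primary endpoint and leaves room for further analyses. Section 3.1 fixes PGA at 3 on entry, so baseline PGA is a constant. The schedule in 4.1.1 and the week-2 list in 4.1.3 show that PGA is scored at the visit where re-randomisation takes place.

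**The concern.** Losing maintenance means reaching PGA 2 or worse, the grade that the appended scale begins with "Mild: Plaque elevation = slight". An almost clear subject is one grade from that point and a clear subject is two. The scale also allows the same upper limit of erythema for almost clear as for mild, so elevation and scaling alone separate those two grades. Week-2 grade is therefore a natural candidate to predict week-8 maintenance, and it is known before allocation.

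At most about 30 subjects can be re-randomised (15 per arm), and fewer if some are not clear or almost clear at week 2. With so few, clear subjects can fall unevenly between Sorilux and vehicle. The trial describes itself as descriptive, so the raw week-8 percentages will probably be read as the main result. Part of the gap between them could then reflect who started clear.

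**Working it through.** The plan gives no power, effect size, responder rate or maintenance rate, so there is no figure to reproduce.

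**Assumptions, none from the documents.** 12 responders, 4 clear and 8 almost clear, 6 per arm. Week-8 maintenance (clear/almost clear) of 80/40, 70/50, 60/40 or 50/50 per cent. No true Sorilux effect.

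**1. Chance of an uneven split (hypergeometric, C(12,6) = 924).**
- 2:2: 6 × 70 / 924 = 45.5%
- 3:1 either way: 2 × 4 × 56 / 924 = 48.5%
- 4:0 either way: 2 × 28 / 924 = 6.1%

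**2. Shift in the crude difference.** With k clear subjects in one arm, shift = gap × 2(k − 2) / 6.
- 3:1: 0.20 × 2/6 = 7 points (70/50); 0.40 × 2/6 = 13 points (80/40)
- 4:0: 0.20 × 4/6 = 13 points; 0.40 × 4/6 = 27 points

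**3. Standard error of the crude difference.** Variance = Σp(1 − p)/36 + gap² × 4 × Var(k)/36, with Var(k) = 6 × (4/12) × (8/12) × (6/11) = 0.727.
- 80/40: (4 × 0.16 + 8 × 0.24)/36 = 0.0711, plus 0.16 × 4 × 0.727/36 = 0.0129. Total 0.0840, SE 0.290.
- 70/50: (4 × 0.21 + 8 × 0.25)/36 = 0.0789, plus 0.04 × 4 × 0.727/36 = 0.0032. Total 0.0821, SE 0.287.

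A 3:1 split therefore moves the result by a quarter (7/29) to just under half (13/29) of the SE.

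**4. Gain from stratified allocation.** With even strata the second term disappears.
- 80/40: 0.0711/0.0840 = 0.85, a 15% reduction
- 70/50: 0.0789/0.0821 = 0.96, a 4% reduction
- 50/50: ratio 1.00, no gain

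With 16 responders, 8 clear, at 80/40, the reduction is 18%. Across the scenarios tried, including odd-sized strata, it is about 1-5% at a 20-point gap and 13-18% at 40 points. It is larger above that (24% at 90/40 with 12 responders, 4 clear). The loss is at most about 3% if grade is not prognostic.

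**5. Stratified analysis without stratified allocation.** For a Mantel-Haenszel difference, the variance given the split is Σw·p(1 − p)/(Σw)², with w = n₁n₀/n per grade. The weights (clear, almost clear) are 1 and 2 at 2:2, 0.75 and 1.875 at 3:1, and 0 and 1.5 at 4:0. Averaging over the split probabilities in step 1:
- 80/40: 0.455 × 0.0711 + 0.485 × 0.0827 + 0.061 × 0.160 = 0.082; ratio to crude 0.98
- 70/50: 0.455 × 0.0789 + 0.485 × 0.0909 + 0.061 × 0.167 = 0.090; ratio 1.10

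The same sum gives a ratio of about 1.08 to 1.09 at 60/40 and 1.13 at 50/50. Analysis alone thus costs about 8-13% in variance when the gap is 20 points or less.

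**6. Bias and test level.** In simulations with 10 to 30 re-randomised and half of them clear, the crude difference averaged zero under no effect. Fisher's exact test rejected in 1.3% to 2.2% of runs.

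**The case against.** Randomisation already deals with chance imbalance on average. The crude difference is unbiased, the 5% level is respected, and a confidence interval covers this variation. That stands. A reader might infer that the primary comparison is biased or its test invalid; the calculations show neither.

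A reader might also be struck that the split is uneven 55% of the time (48.5% + 6.1%). Most of that is 3:1, one subject away from balance, with a shift under half the standard error. Only the 4:0 tail or a large gap between grades gives a shift close to the standard error.

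Nor do the documents prescribe one unstratified list for week 2. Section 4.2.2 describes assignment at entry, and the plan is silent on the later step. No effect size is stated, so the shift cannot be called comparable to the expected effect. How strongly grade predicts maintenance is also unknown. The scale's line between clear and almost clear is soft, and the grade may discriminate weakly.

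Finally, the study calls itself exploratory, and initial group could compete as a second stratification factor; crossing both would give four cells for perhaps 12 subjects. This argues for one factor only and against treating the point as a serious defect. It does not remove the case for using a relevant value that is already collected. Leaving adjustment to the further analyses that 7.2 permits would mean choosing it after the split is known.

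**Conclusion.** The point holds as a cheap improvement, not as a flaw that invalidates the trial. The plan does not use week-2 PGA in allocation or analysis, and the one covariate it names is constant for PGA. The consequence is avoidable noise in a single small trial: 7 to 13 points for a 3:1 split and 13 to 27 points for a 4:0 split, against a standard error of about 29 points. The sizes rest on assumed numbers of responders and clear subjects and on assumed maintenance rates; with no gap between grades the shift is zero. Stratifying makes the arms more comparable but does not cure the imprecision of a trial this small.

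**What to change.** In sections 2 and 4.2.2, state that the 1:1 re-randomisation is stratified by week-2 PGA (0 v 1), using two short lists in small blocks, with assignment made only after the week-2 PGA is recorded. In 7.2, state that week-8 maintenance will be shown by arm within each week-2 grade, and that the Sorilux-vehicle difference will be estimated stratified by that grade, with a confidence interval.

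The cost is one extra list and a sentence or two. The dispenser must be told the grade, and an odd-sized stratum can leave a one-subject imbalance.

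If the lists are already made, tabulate week-8 maintenance by week-2 grade and present the stratified difference only as a sensitivity analysis, because of the precision loss shown above.

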### Dispensation and Dosage Schedule

A 2-week supply of study medication will be dispensed at baseline and applied per instructions. A new supply will be given for 6 weeks per re-randomization.

Lexette foam will be applied twice daily and Sorilux foam will be applied twice daily 5 minutes after the Lexette application.

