## **7 STATISTICS**

### **7.1 Sample Size Justification**

This is a descriptive study and a formal justification for the sample size is not necessary.

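### Should the week-2 re-randomisation be stratified by induction group, and week-8 results be pre-specified by treatment sequence?

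*Combined protocol and SAP*

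**What the plan says.** The Study Objective speaks of the "additional benefit of Lexette and Sorilux in the beginning and then maintenance treatment of Sorilux alone". Section 1.1 frames the second stage as "maintenance of success compared to vehicle with Sorilux for the next 6 weeks", with the percentage still clear or almost clear on PGA at week 8 as the primary endpoint.

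Under Section 2, "Approximately 30 qualified subjects will be enrolled into a 8 weeks study", 15 in Group A and 15 in Group B. Week-2 responders from both groups are "re-randomized into Sorilux for 6 weeks versus vehicle for 6 weeks at 1:1 ratio". The dispensing section adds only that "A new supply will be given for 6 weeks per re-randomization". Section 4.2.2 describes a balanced 1:1 schedule, "available only to the member(s) of the site staff that is responsible for dispensing study treatment to the subject", and mentions no strata, blocks or second-stage list.

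Section 7.1 states "This is a descriptive study". Section 7.2 plans frequencies for all categorical variables and then leaves the rest open: "Any additional statistical analyses will be performed as appropriate and detailed in the final report". It does not say how week-8 results are grouped for subjects who by then have had two randomised assignments.

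**The concern.** Responders can follow four paths: A then Sorilux, A then vehicle, B then Sorilux, B then vehicle. Read literally, the objective describes the first. A pooled Sorilux maintenance arm mixes it with the third. With 7 Group A and 5 Group B responders (assumed), on average 5/12 = 42% of that arm would have had no Sorilux during induction.

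With so few subjects, an unstratified re-randomisation can also split Group A unevenly between the maintenance arms. If two weeks of earlier Sorilux affects how well response is held, that imbalance feeds into the crude Sorilux-vehicle difference, and the sequence of most interest could end up with very few subjects. The usual remedy is one allocation list per first-stage group and a named table by sequence. Both look nearly free.

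**Working it through.** **Inputs.** From Section 2: 15 + 15 = 30 subjects, which agrees with the stated total, and 1:1 at each stage. The plan gives no other figure to reproduce. The documents give no week-2 success rate and no maintenance rate, so these are assumptions: 7 Group A and 5 Group B responders (7/15 = 47% and 5/15 = 33%); maintenance rates pA and pB averaging 55% and differing by a gap g; no treatment effect. One list gives 6 per arm. Two lists use permuted blocks of 2 and 4.

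**Step 1: chance imbalance with one list.** There are C(12,6) = 924 equally likely splits. The number with k Group A subjects on Sorilux is C(7,k) × C(5,6−k): 7, 105, 350, 350, 105, 7 for k = 1 to 6.

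- Arms 3 or more Group A subjects apart: (7 + 105 + 105 + 7)/924 = 24.2%.
- Best split, 4 v 3: 700/924 = 75.8%.
- Two or fewer subjects on A then Sorilux: 112/924 = 12.1%.
- Root-mean-square difference in Group A share between arms: 0.297, against 0.120 with two lists.

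The typical shift in the crude difference is g × 0.297, or 3.0, 5.9 and 8.9 points for gaps of 10, 20 and 30. This shift is one component of the sampling error, not an addition to it, as Step 2 shows.

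**Step 2: does stratifying buy precision?** Write vA = pA(1 − pA) and vB = pB(1 − pB).

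One list, crude difference: variance = (0.297g)² + (7vA + 5vB)/36.

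Two lists, Mantel-Haenszel difference: 7 and 5 are odd, so the groups always split 4 v 3 and 3 v 2. The weights are 3×4/7 = 1.714 and 2×3/5 = 1.200, which sum to 2.914. Variance = (1.714vA + 1.200vB)/2.914².

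- Gap 0 (55%, 55%): crude 0.2475 × 12/36 = 0.0825, SE 28.7 points. Stratified 0.2475/2.914 = 0.0849, SE 29.1.
- Gap 30 (70%, 40%): crude 0.0080 + (7×0.21 + 5×0.24)/36 = 0.0080 + 0.0742 = 0.0821, SE 28.7. Stratified (1.714×0.21 + 1.200×0.24)/8.493 = 0.0763, SE 27.6.

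| Gap A−B (points) | One list, crude SE | Two lists, Mantel-Haenszel SE |
|---|---|---|
| 0 | 28.7 | 29.1 |
| 10 | 28.7 | 28.9 |
| 15 | 28.7 | 28.7 |
| 20 | 28.7 | 28.4 |
| 30 | 28.7 | 27.6 |

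The loss at small gaps arises because odd-sized lists cannot split evenly: the weights sum to 2.914 instead of the 6×6/12 = 3 of two equal arms. Half the time both odd subjects land in the same arm, and the arms are 7 v 5.

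With 5 and 3 responders stratifying is worse at gaps of 0, 10 and 20 points (35.2 to 36.4, 35.1 to 36.1, 35.05 to 35.45). With 11 and 9 it starts to help at a gap of about 10.

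**Step 3: what a table by sequence could show.** Expected cell size is 15 × week-2 success rate / 2. Assumed rates of 30% (A) and 20% (B) give 2.3 and 1.5 subjects per cell; 50% and 30% give 3.8 and 2.3; 80% and 60% give 6.0 and 4.5. Exact 95% intervals for a single cell are 9% to 99% for 2 of 3, 7% to 93% for 2 of 4, and 12% to 88% for 3 of 6.

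**The case for a change.** The best case for a change is about reporting. In a descriptive study the tables are the result, the objective describes a sequence, and choosing the week-8 grouping after unblinding, with cells of about three subjects, is not the same as naming it beforehand. Separate lists would also steady the cells: with 7 and 5 responders, A then Sorilux would always have 3 or 4 subjects instead of anywhere from 1 to 6. With 8 and 4 responders on one list, some cell has one subject or none 55% of the time. The schedule is already confined to dispensing staff, so separate lists need not threaten the blind.

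Much of this is true. The plan does not state the grouping, and separate lists do limit chance imbalance. But the objective can equally be read as two stages: A against B at week 2 (PGA at week 2 is a secondary endpoint), then Sorilux against vehicle among responders. Section 1.1 defines the second comparison in exactly those terms. The four-way table is not excluded. Provided both assignments are recorded for each subject, it can be produced at reporting with nothing lost. Steadier cells of 3 or 4 still carry intervals that rule out almost nothing.

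**Conclusion.** No change follows. Missing strata introduce no bias, because the re-randomisation protects the Sorilux-vehicle comparison on average, and the pooled result is a legitimate answer to Section 1.1.

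Stratifying is a trade-off. At 7 and 5 responders it raises the standard error by about 1.5% (29.1 against 28.7) if first-stage group makes no difference, breaks even at a gap of about 15 points, and lowers it by about 3.6% (27.6 against 28.7) at 30 points. It also leaves the arms 7 v 5 half the time. These figures rest on assumed responder counts and maintenance rates, and the documents do not say whether earlier Sorilux affects maintenance. A statistician could reasonably go either way.

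The missing table by sequence is a gap in detail. The planned frequencies and the allowance for further analyses in Section 7.2 cover it, and cells this small would support description only.

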## **Blinding**

Study treatments will be provided to subjects in a blinded-label manner . Investigator will be blinded.

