### **4.2.4 Supplies and Accountability**

The Investigator or pharmacist will inventory and acknowledge receipt of all shipments of study medication. All study medication must be kept in a locked area with access restricted to designated study personnel. The study medication must be stored in accordance with the instructions provided with the shipment. The Investigator or pharmacist will also keep accurate records of the quantities of study medication dispensed and returned by each subject.

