### **8.5 Data Handling and Record Keeping**

Investigators must ensure that proper source documentation for all study activities are diligently maintained and securely kept. Investigators will transfer all relevant data from source documents to the Case Report Form as stipulated in this Study Protocol and his/her signature on the Case Report Form guarantees completeness and integrity of these data. Investigators will maintain reliable study device dispensing/dosing records and will store study supplies in a secure, locked location. In addition, Investigators will ensure that all study-related source documentation and Case Report Forms will be maintained for a period of two years after the conclusion of the study.

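### Section 2 labels medication by a group whose contents the protocol prints, which conflicts with the blinded label and blinded investigator and could unblind the week-2 grades

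*Combined protocol and SAP*

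**What the plan says.** All places are in the combined protocol and SAP.

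- **Section 2, Study Design:** "This is a single-center, double-blind study". A small table defines Group A, "Lexette + Sorilux for 2 weeks", and Group B, Lexette with vehicle foam for the same period. The text below the table says that "the medications will be labelled for the appropriate group as noted above".
- **Blinding:** "Study treatments will be provided to subjects in a blinded-label manner", and "Investigator will be blinded". What the label shows is not stated.
- **4.2.2, Treatment Assignment:** subjects are randomised through TANs, and the schedule "will be available only to the member(s) of the site staff that is responsible for dispensing study treatment to the subject".
- **4.2.4, Supplies and Accountability:** "The Investigator or pharmacist will also keep accurate records of the quantities of study medication dispensed and returned by each subject".
- **8.5, Data Handling and Record Keeping:** "Investigators will maintain reliable study device dispensing/dosing records", with no pharmacist as an alternative.
- **5.2, 5.3 and the assessment schedule in 4.1.1:** the investigator grades PGA, TLSS and BSA.
- **Section 2 and 1.1:** the week-2 PGA decides who is re-randomised to Sorilux or vehicle. The primary endpoint is the PGA at week 8.

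**The concern.** The groups to which the labelling sentence refers are the two in the table just above it, and that table gives their contents. A can marked for its group would tell any protocol holder, including the investigator, what the subject receives in weeks 0 to 2.

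The investigator is also the grader, and PGA is a judgement. In the appended PGA scale, grades 1 and 2 carry the same erythema limit. The line between them therefore rests on whether slight elevation is doubtful or definite and on how dryness is told from fine scale. That line separates responders from non-responders.

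At week 2 the PGA is both a secondary endpoint and the gate to the maintenance phase. A grader who knows the arm could, without intending it, shift the week-2 comparison of Group A with Group B and the list of subjects declared responders. TLSS and BSA at week 2 are graded by the same person and are open to the same influence.

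**Working it through.** The protocol gives no figure on this point, so the check is a comparison of texts.

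**1. What the label shows.** Section 2 ties the label to the group, and the group is decoded on the same page. The Blinding section says the label is blinded. Nothing else in the document says whether the can carries a letter, a product name or a TAN. On the literal reading of section 2, the two statements cannot both be met for someone who holds the protocol.

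**2. Who may know the allocation.** Under 4.2.2 the schedule is confined to staff who dispense. No passage says that those staff do not grade. The Blinding section requires the investigator not to know.

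**3. Who handles supplies and records.**
- 4.2.4 names the investigator or the pharmacist, so it permits the investigator to keep the records but does not require it.
- 8.5 gives dispensing records to investigators outright.
- Both concern quantities or dispensing in general. Both groups receive Lexette and a second foam, so quantities alone do not show which foam it was. The records reveal the arm only if they carry a group label, or if whoever keeps them also holds the schedule.

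**4. Which grades are reached.**
- *Week 2:* the A/B table covers weeks 0 to 2, so a group label bears directly on PGA, TLSS and BSA at this visit.
- *Week 8:* responders are re-randomised 1:1. Under such an allocation, knowing that a subject started in A or B says nothing about the maintenance arm. The gate also precedes re-randomisation, so subjects wrongly let in or kept out are not steered towards one maintenance arm. Who is studied may change, but the Sorilux-versus-vehicle contrast is not biased by that step alone. How cans are labelled in weeks 2 to 8 is not described.

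**5. Scale.** With n = 15 per group (section 2), one subject's weight in a week-2 response rate is 1/15 = 0.067, or 6.7 percentage points. One PGA recorded as 1 rather than 2 moves that group's rate by this amount and adds one subject to the maintenance phase. This is the leverage of a single grade. It says nothing about how often a grade would be affected.

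**The case against.** The strongest reply is that the passages can be read together without conflict. Section 2 does not say that a letter or product name is printed on the can. Labelling for the appropriate group may only mean that cans are prepared for the assigned arm under a code, with the TANs of 4.2.2 supplying the code and the Blinding section confirming it. The record-keeping duties would then be harmless: 4.2.4 offers the pharmacist, 8.5 is generic wording (it speaks of a device in a trial of foams), and quantities of coded cans do not identify a foam.

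Much of this stands. The benign reading is possible, and it rules out saying that the investigator will be unblinded. It does not settle the matter, because no passage states it and section 2, taken as written, points the other way.

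A reader might infer three stronger claims, which the documents do not support:

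- *That every investigator-graded endpoint at weeks 2 and 8, including the primary endpoint, is exposed.* The group key stops at week 2, and re-randomisation follows the week-2 PGA.
- *That the return and weighing of cans shows them to the grader.* The visit lists in 4.1 and the compliance text in 4.2.5 do not say who weighs them. Sharing a visit with the grading is not evidence that the grader handles them.
- *That 6.7 points is the size of the bias.* It is one subject's share of a group of 15.

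The descriptive, exploratory status in section 7 answers a question about sample size. It does not protect a subjective grade from a grader who knows the arm.

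**Conclusion.** The point holds as an unreconciled conflict with a limited reach. The labelling sentence in section 2, taken literally, contradicts the Blinding section, and nothing separates the grader from the dispensing role or from records that might show treatment identity. What is at risk is the set of week-2 PGA, TLSS and BSA grades, and through them the week-2 comparison and the declaration of responders.

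The week-8 comparison of the re-randomised arms is not biased by this alone. For that phase the defect is an omission: labelling is not described.

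No size of bias can be given. The conclusion assumes that the labelling sentence means what it says, that the grading investigator has the protocol to hand, and that the primary comparison is between the re-randomised arms, as 1.1 indicates. If coded labels were always intended, the problem is one of wording and the same edit resolves it. The change should be made before supplies are labelled.

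**What to change.** 1. **Section 2:** replace the labelling sentence. Cans carry the TAN only, with a new TAN issued at re-randomisation. In neither phase do they carry a group letter or a product name that distinguishes Sorilux from vehicle.
2. **4.2.2 and Blinding:** state that the staff who hold the schedule and dispense do not grade PGA, TLSS or BSA, and that the grader has no access to the schedule or to any record that shows treatment identity.
3. **4.2.4 and 8.5:** bring the record-keeping duties into line with that statement. The grading investigator may keep overall responsibility for the records, provided that any record showing treatment identity is held by the dispensing staff.

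The cost is protocol and label wording. TANs and a dispensing role already exist in 4.2.2, and no visit, subject or treatment changes. The small downside is that the grading investigator cannot cover dispensing. 4.2.2 does not say whether the present dispensing staff are free of grading duties, so the site should confirm that two people are available.
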